#### **3.3.2. Analyses of the Aggregated N-of-1 Trials**

For the aggregation of the N-of-1 trials, a Bayesian multi-level model will be applied to assess the efficacy of OLP relative to no treatment in reducing discontinuation symptoms (primary outcome) at population-level. We will utilize multi-level mixed models to estimate the posterior distribution of the population-level average treatment effect and the within- and between-patient variance. Additionally, we will obtain a pooled estimate of the individual-level patient's

treatment effect. For the aggregated analysis, noninformative priors will be selected for all parameters, as there was no prior information available before the study that allowed a reasonable effect estimate of OLP treatment in reducing discontinuation symptoms. The dependence of responses over time will be modeled with an AR1 error structure. Similarly, to the individual-level model described above, we will obtain estimates of the posterior distribution of the average OLP treatment effect on the population-level in reducing discontinuation symptoms. Extensions to the above model will be applied to account for time trends. Further, we will assess between-patient covariates such as age, female gender, prior negative pre-experiences with discontinuation, intensity of discontinuation symptoms over the course, higher maintenance dose, and duration of antidepressant use to determine if the given outcome is related to such variables. From the aggregated Bayesian analysis, we derive the posterior distribution of the mean difference between the outcomes of OLP and no treatment. Secondary outcomes will be modelled in the same manner. Statistical analyses will be performed in JAGS running from R, using the Markov Chain Monte Carlo (MCMC) method to obtain empirical samples from the joint posterior distribution of the parameters. Secondary outcomes such as dysfunctional treatment expectations, depressed mood, and anhedonia will be modelled in the same manner.

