### 1.2. Overall Study Aims

Aim 1: To obtain individual-level and population-level effect estimates of the average efficacy of OLP relative to no treatment in reducing antidepressant discontinuation symptoms (primary outcome), and in improving dysfunctional treatment expectation, depressed mood, and anhedonia (secondary outcomes) based on a series of N-of-1 trials.

Aim 2: To explore factors that modify the efficacy of OLP, i.e., age, female sex, prior negative experiences with discontinuation, discontinuation symptom load over the discontinuation period and higher maintenance dose and longer duration of antidepressant use.

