## 2.5. Timing of Outcome Assessments

**Table 1:** Schedule of enrollment, intervention, and assessments according to SPIRIT-PRO

	STUDY PERIOD						
	Phase 1: Screening & Eligibility		Phase 2: Discontinuation		Phase 3: N-of-1 trials		Phase 4: Follow-up
Timepoint	S1	S2	T0	T1-T5	T6-T8	T9	FU1
Week	-2	-1	0	1/2/3/4/5	7/9/11	13	26
Enrolment:							
Eligibility screen	✓	✓					
Informed consent		✓					
Initial consultation							
prescribing physician		✓					
Allocation (N-of-1 trials)					✓ (T5)		
Interventions:							

Run-In (1 week)		↔				
Discontinuation phase (4 weeks)			↔			
N-of-1 trials (8 weeks)				↔		
Assessments:						
Primary outcome (‘StudyU’)						
Discontinuation symptoms (GEEE ACT )				↔		
Secondary outcomes (‘StudyU’)						
Treatment expectations (GEEE EXP )				↔		
Depressed mood and anhedonia (PHQ-2)				↔		
Effect modifiers (‘LimeSurvey’ and clinical interviews)						
Gender			✓			
Maintenance dose of antidepressant medication	✓					
Duration of antidepressant use	✓					
Prior negative experiences with discontinuation of antidepressant medication (GEEE PRE )*			✓			
Discontinuation symptom load over the discontinuation period (DESS)		✓	✓			
Other pre-specified outcomes (‘LimeSurvey’ and clinical interviews)						
Discontinuation symptoms (DESS)		✓	✓	✓	✓	✓
Current treatment effects (GEEE ACT )			✓	✓	✓	✓
Expert-rated depressive symptoms (MADRS+)*	✓	✓	✓	✓	✓	✓

Self-reported depressive symptoms (BDI-II)*	✓	✓	✓	✓	✓	✓
Recurrence			✓	✓	✓	✓
Well-being (SWEMWBS)		✓	✓	✓	✓	✓
Adherence (single item)		✓	✓	✓	✓	✓
Adverse events (single safety items)		✓	✓	✓	✓	✓
Treatment expectations (TEX-Q, GEEEEXP)*		✓	✓	✓	✓	✓
Psychopathology (SCID-5-CV)*	✓					
Demographic* & medical characteristics	✓	✓				
Anxiety vs. Depression (STADI Trait/State)*			✓			
Psychophysiological stress (PSS-10)*			✓			
Prior treatment experience (DESSPAST)			✓			
Side-effects of antidepressant medication (GASE)*			✓		✓	
Antidepressant medication blood serum level				✓ (T1)	✓	

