#### **3.3.1. Analyses of Individual N-of-1 Trials**

At the end of the individual N-of-1 trials, statistical analyses will be applied to compare the outcomes of OLP vs no treatment. Bayesian models will be utilized to compare the average ratings of discontinuation symptoms (primary outcome) during the periods of OLP treatment periods to those with no treatment. These obtained estimates of individual-level effects can be viewed as naïve estimates as they do not incorporate information from the other participants. We will include a first-order autoregressive (AR1) error structure to acknowledge that measurements at adjacent times show a higher correlation than measurements far apart in time, given the longitudinal nature of our data. Non-informative priors will be selected for all parameters, as no prior information was available before the study that allowed a reasonable effect estimate of OLP treatment in reducing discontinuation symptoms. Separate analyses will be conducted for each individual to compare the average response to treatment. Based on this model, we will obtain estimates of the posterior distribution of the average OLP treatment effect in reducing discontinuation symptoms on an individual level. Secondary outcomes such as dysfunctional treatment expectations, depressed mood, and anhedonia will be analyzed similarly.

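### Aim 2 asks what modifies the OLP effect, but the SAP states only a covariate–outcome association and no treatment-by-covariate interaction

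*SAP*

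**What the plan says.** Section 1.2 sets Aim 2 as "To explore factors that modify the efficacy of OLP" and names six factors: age, sex, earlier bad experience with stopping, symptom load while stopping, dose and length of use. Table 1 in section 2.5 lists five of them (all but age) under "Effect modifiers".

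The only analysis text for these factors is one sentence in section 3.3.2. It says that between-patient covariates will be assessed "to determine if the given outcome is related to such variables". The only other model extension named there is for time trends. No section mentions an interaction, a covariate on the treatment slope, a subgroup contrast, or a regression of individual effects on the factors. Section 3.3.2 adds: "Secondary outcomes will be modelled in the same manner".

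One factor is also worded differently in two places. Section 3.3.2 has "intensity of discontinuation symptoms over the course", while section 1.2 has "discontinuation symptom load over the discontinuation period". Table 1 agrees with section 1.2 and names the DESS as the instrument.

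**The concern.** Effect modification concerns the difference between OLP and no treatment. A relation between a covariate and the outcome concerns the level of the score. These are different parameters, and the first cannot be read off the second.

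A programmer who follows section 3.3.2 literally would fit a covariate main effect. A factor that raises symptoms equally in both conditions could then be reported as the Aim 2 finding although it modifies nothing. A true modifier would get a coefficient that is not the modification. That coefficient would also depend on the treatment coding and on the intercept–slope covariance, neither of which the SAP states. The same would carry over to the secondary outcomes.

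If symptom intensity over the course were taken to include the N-of-1 phase, that covariate would also overlap with the outcome it is meant to explain.

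**Working it through.** **What outcome means in this SAP.** Section 3.3.1 says the individual analyses will "compare the outcomes of OLP vs no treatment". In section 3.3.2 the sentence directly after the covariate sentence describes the effect as the "mean difference between the outcomes of OLP and no treatment". In both places the outcome is the score under a condition and the effect is a difference between outcomes. On that usage, relating the outcome to a covariate is a main effect.

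**Inputs from sections 2.1 to 2.3.** 18 patients; ABAB or BABA allocated 1:1; 112 ratings each (28 per period); AR(1) correlation 0.7; random-slope variance 0.75; residual error 1.5, read both as a variance (1.5) and as an SD (variance 2.25); target difference 0.8 points; 5% significance level. Paired results below follow the order variance / SD.

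**Assumptions, not in the SAP.** Two-sided testing; a binary factor split 9/9 (also 6/12); intercept variance 0, 1, 2 or 4; intercept–slope correlation −0.3, 0 or +0.3. With both residual readings this makes 20 settings.

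**Step 1: the SAP's own power figure.** Generalised least squares within one patient (0/1 coding) gives a variance of the effect estimate V_bb = 0.1619 / 0.2429 and a covariance with the intercept V_ab = −0.0810 / −0.1214.
- SE of the mean effect = √[(0.75 + V_bb)/18] = √(0.9119/18) = 0.225, or √(0.9929/18) = 0.235.
- Power = Φ(0.8/SE − 1.96) = 94.5% / 92.6%, against 93% stated. The set-up reproduces the plan.

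**Step 2: main effect only.** Let G_ab be the intercept–slope covariance. If the two factor levels differ by d_a in level under no treatment and by d_b in OLP effect, a model that forces d_b to zero estimates

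coefficient = d_a − d_b × (V_ab + G_ab)/(V_bb + 0.75).

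- Purely prognostic factor (d_a = 0.8, d_b = 0): 0.80 in all 20 settings.
- Pure modifier (d_a = 0, d_b = 0.8), G_ab = 0: 0.8 × 0.0810/0.9119 = 0.071, or 0.8 × 0.1214/0.9929 = 0.098.
- Same modifier, −0.5/+0.5 coding, G_ab = 0: 0.40. The mid-level differs by half of 0.8, and V_ab becomes −0.0810 + ½ × 0.1619 ≈ 0.
- Same modifier, intercept variance 2, correlation ∓0.3, so G_ab = ∓0.3 × √(2 × 0.75) = ∓0.367:

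| Coding | Correlation −0.3 | Correlation +0.3 |
|---|---|---|
| 0/1 | 0.393 / 0.394 | −0.251 / −0.198 |
| −0.5/+0.5 | 0.722 / 0.696 | 0.078 / 0.104 |

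Intercept variance 4 widens the ranges to 0.527 to −0.385 (0/1) and 0.856 to −0.056 (centred), with residual variance 1.5.

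**Step 3: with an interaction term.** The interaction is 0.80 for the modifier and 0.00 for the prognostic factor in all 20 settings.

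**Step 4: precision of the interaction.** With share p in one level, SE = √[(0.75 + V_bb)/(18 p(1−p))]. The difference detectable with 80% power is 2.80 × SE (1.96 + 0.84).
- 9/9: √(0.9119/4.5) = 0.450 and √(0.9929/4.5) = 0.470; detectable 1.26 / 1.32 points.
- 6/12: √(0.9119/4) = 0.477 and √(0.9929/4) = 0.498; detectable 1.34 / 1.40 points.
- Power for a 0.8-point modification with a 9/9 factor: Φ(0.8/SE − 1.96) = 43% / 40%.

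**The case against.** The strongest reply is that the covariate sentence is loosely worded rather than wrong. Aim 2 and the Table 1 heading both point to modification, the sentence does not say that a main-effect coefficient will be the Aim 2 result, and the model also yields pooled individual effects that could be related to the factors. This stands in part: an interaction may well have been intended, and the protocol, not seen here, may give one. But the SAP states none, and its own use of outcome in the neighbouring sentence supports the literal reading. On the charitable reading the clause still needs changing.

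A second reply is that the wide ranges come from intercept variances and correlations that are not in the SAP. That is true. They show only that the coefficient is not a stable measure of modification. The core contrast, 0.80 for a non-modifier against 0.07 to 0.10 or 0.40 for a real modifier, does not need them.

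Third, section 2.3 assumes a fixed intercept for the sample size. If that means one intercept per patient, a between-patient main effect cannot be estimated and the factors could enter only through the treatment slope. The SAP does not say so. In that case the analysis in section 3.3.2, read literally, could not be fitted, while the interaction still could. The fix should allow for this.

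Finally, Aim 2 is exploratory and the interaction has low power. That limits how serious the point is, but an imprecise estimate of the right quantity serves an exploratory aim better than an estimate of another one.

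**Conclusion.** The concern holds. The analysis stated for the Aim 2 factors does not match the aim: it addresses symptom level, not the OLP effect. For a 0.8-point factor, the literal analysis returns 0.80 when there is no modification. When the modification is real it returns 0.07 to 0.10 (0/1 coding) or 0.40 (centred coding) at zero intercept–slope covariance, and under some assumed covariances the sign reverses.

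The textual conclusion needs no numerical assumption. The sizes rest on the SAP's planning values, a binary 9/9 factor and the main-effect reading of the sentence. The mismatch should be corrected before analysis. It touches one of two aims and extends to the secondary outcomes, but leaves the Aim 1 estimates and the sample size as they are. The differing description of the symptom-load factor is a minor wording point.

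**What to change.** In section 3.3.2, replace the clause on relating the outcome to the covariates. State that each listed factor enters the multi-level model one at a time, as a treatment-by-covariate interaction (the covariate acting on the patient-level treatment slope), together with its main effect where the intercept structure allows one. Name the posterior and credible interval of the interaction as the exploratory Aim 2 result, and say whether the secondary outcomes get the same terms. In the same sentence, describe the symptom factor as in section 1.2 and Table 1: DESS load over the discontinuation period.

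The cost is one clause, one wording alignment and one interaction term per factor, with no new data. The drawback is imprecision: with 18 patients a 9/9 factor must change the OLP effect by about 1.3 points for 80% detection, more than 1.5 times the 0.8-point minimally important difference (1.26/0.8 = 1.6). The SAP should say so, so that wide intervals are not read as absence of modification.

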### 3.4. Protocol deviations

Treatment adherence to the intake of the OLP pills during the experimental phase (N-of-1 trials) is assessed at study visits by a single item inquiring how many times the placebo pill was taken since the last study visit.

Major protocol deviations include:

- Withdrawal of informed consent
- Pregnancy
- Insufficient treatment adherence regarding requirements for the study participation (intake of at least 80% of placebo pills during OLP treatment phase) (Nestoriuc et al. 2016)
- Restarting of antidepressant use during experimental phase.

### 3.5. Missing Data

We will disregard missing values in the analyses and perform complete-case analyses, hence we are assuming that missing values are missing completely at random. In case of major protocol deviations before the end of the N-of-1 trial, we will analyze all available data.

### **3.6. Analysis Populations**

#### **3.6.1. Intention-To-Treat (ITT)**

The primary analyses are based on the ITT population, i.e., all randomized patients are included, regardless of whether they completed the whole study period and received the allocated intervention. For patients that dropped out of the study or that restarted the use of antidepressant medication during the N-of-1 trial, their recorded data until that timepoint will be included in the analyses.

#### **3.6.2. Per Protocol (PP)**

The sensitivity analysis is based on the per protocol population, i.e., all randomized patients, who have no major protocol violations and completed the whole study (i.e., compliance to ambulatory assessment >50% in the eight-week N-of-1 trial).

### **3.7. Safety and Adverse Events (AE)**

Treatment will be terminated in case of patient's withdrawal of the informed consent, pregnancy and objections by study staff based on pre-defined health risks. These include treatment-related serious AEs (SAEs), recurrence of major depression, acute suicidality, and severe discontinuation symptoms. Safety-relevant outcomes will be evaluated at every study visit by trained study staff.

A data safety monitoring board (DSMB) will advise and review the proposed study. Study-related AEs, drop-outs due to AEs, medical events and mortalities will be reported immediately (within 48 hours). The DSMB will receive information about safety-relevant outcomes regularly.

## **4. Statistical Software**

- JAGS version 4.3.0 or newer
- R version 4.2.2 or newer

